NON-INTERVENTIONAL (NI) STUDY PROTOCOL

Study information

Title	A Post-Authorization Safety Study of Atrial Fibrillation Following Respiratory Syncytial Virus Vaccine (ABRYSVO TM) Among Adults Aged 18 Years and Older in the Veterans Affairs Health			
	System			
Protocol number	C3671037			
Protocol version identifier	2.0			
Date	04 December 2024			
European Union (EU) Post Authorization Study (PAS) register number	EUPAS1000000290			
Active substance	ABRYSVO TM is a bivalent recombinant stabilized prefusion F (preF) protein subunit vaccine (Respiratory Syncytial Virus Vaccine). It consists of equal amounts of preF antigens from the two major respiratory syncytial virus (RSV) subgroups: RSV subgroup A preF (60 µg) and RSV subgroup B preF (60 µg).			
Medicinal product	Respiratory Syncytial Virus Bivalent Stabilized Prefusion F Subunit Vaccine (ABRYSVO TM , Respiratory Syncytial Virus Vaccine)			
Research question and objectives	Research question: What are the incidence rates of atrial fibrillation and supraventricular arrhythmia, overall and in subcohorts of interest, among individuals vaccinated with ABRYSVO within the United States (US) Veterans Health Administration (VHA) system as compared to expected rates of those events?			
	Primary study objective:			
	 To estimate the incidence of atrial fibrillation following administration of ABRYSVO among adults 18 years of age and older in the VHA system 			
	Secondary study objectives:			

	 To estimate the incidence of supraventricular arrhythmia following administration of ABRYSVO among adults 18 years of age and older in the VHA system To assess whether adults 18 years of age and older in the VHA system experience increased risk of atrial fibrillation and supraventricular arrhythmia following administration of ABRYSVO To estimate the incidence of atrial fibrillation and supraventricular arrhythmia in sub-cohorts of interest (ie, individuals with specific conditions that increase the risk for severe RSV, older age groups [60 to 69 years, 70 to 79 years, ≥80 years], individuals in VA priority group 1, individuals with dual VHA/Medicare coverage, females, individuals with co-administration with other vaccines) in the VHA system following administration of ABRYSVO To assess whether sub-cohorts of interest (ie, individuals with specific conditions that increase the risk for severe RSV, older age groups [60 to 69 years, 70 to 79 years, ≥80 years], individuals in VA priority group 1, individuals with dual VHA/Medicare coverage, females, individuals with co-administration with other vaccines) in the VHA system experience increased risk of atrial fibrillation and supraventricular
Country(ies) of	arrhythmia following administration of ABRYSVO US
study	
Author	[name], PhD Deputy Associate Chief of Staff/Research Veterans Affairs Medical Center White River Junction, VT [name] Epidemiologist, Clinical Epidemiology Program Veterans Affairs Medical Center White River Junction, VT [name], ScD, MS

Safety Surveillance Research
Worldwide Medical and Safety
Pfizer, Inc.
New York, NY

[name], MPH
Managing Principal and Chief Epidemiologist
Analysis Group, Inc.
Boston, MA

[name]
Managing Principal Analysis Group, Inc.
Los Angeles, CA

This document contains confidential information belonging to Pfizer. Except as otherwise agreed to in writing, by accepting or reviewing this document, you agree to hold this information in confidence and not copy or disclose it to others (except where required by applicable law) or use it for unauthorized purposes. In the event of any actual or suspected breach of this obligation, Pfizer must be promptly notified.

2. LIST OF ABBREVIATIONS

Abbreviation	Definition
ABRYSVO	Respiratory Syncytial Virus Vaccine
AE	Adverse event
AEM	Adverse event monitoring
AHA	American Heart Association
AIDS	Acquired immunodeficiency syndrome
AR	Adverse reaction
ATT	Average treatment effect among the treated
BMI	Body mass index
CAD	Coronary artery disease
CAR	Chimeric antigen receptor
CBER	Center for Biologics Evaluation and Research
CCI	Charlson Comorbidity Index
CDC	Centers for Disease Prevention and Control
CDW	Corporate Data Warehouse
CEP	Clinical Epidemiology Program
CHF	Congestive heart failure
CI	Confidence interval
CMS	Centers for Medicare & Medicaid Services
COPD	Chronic obstructive pulmonary disease
COVID-19	Coronavirus Disease 19
СРТ	Current Procedural Terminology
CRF	Case report form
EC	Ethics Committee

Abbreviation	Definition
ED	Emergency department
EHR	Electronic health record
EMA	European Medicines Agency
EU	European Union
FDA	Food and Drug Administration
FFS	Fee-For-Service
GEP	Good Epidemiological Practice
GPP	Guidelines for Good Pharmacoepidemiology Practices
HBV	Hepatitis B virus
HCPCS	Healthcare Common Procedure Coding System
НСТ	Hematopoietic cell transplant
HCV	Hepatitis C virus
HIV	Human immunodeficiency virus
HMA	Heads of Medicines Agencies
HPV	Human papillomavirus
HSCT	Hematopoietic stem cell transplant
ICD-10-CM	International Classification of Diseases, Tenth Revision, Clinical Modification
ICD-10-PCS	International Classification of Diseases, Tenth Revision, Procedure Coding System
IEA	International Epidemiological Association
IP	Inpatient
IQR	Interquartile range
IRB	Institutional Review Board
IRR	Incidence rate ratio

Abbreviation	Definition
LRTD	Lower respiratory tract disease
MBSF	Master Beneficiary Summary File
MenACWY	Meningococcal conjugate vaccine
MenB	Serogroup B meningococcal vaccine
mRNA-1345	Messenger Ribonucleic Acid-1345 Vaccine
MONeT	RSV IMmunizatiON Study for AdulTs at Higher Risk of Severe Illness
MVA-BN-RSV	Modified Vaccinia Ankara-Bavarian Nordic-Respiratory Syncytial Virus Vaccine
NDC	National Drug Codes
NI	Non-interventional
NIS	Non-interventional study
NSAID	Nonsteroidal anti-inflammatory drug
OP	Outpatient
PAS	Post Authorization Study
PASS	Post-authorization safety studies
PCR	Polymerase chain reaction
PDE	Prescription Drug Event
PPV	Positive predictive value
preF	Prefusion F
PS	Propensity score
RDC	Research and Development Committee
RENOIR	RSV vaccine Efficacy study iN Older adults Immunized against RSV disease
RR	Risk ratio

Abbreviation	Definition
RSV	Respiratory syncytial virus
RSV F	Respiratory Syncytial Virus Fusion Nanoparticle Vaccine
RSVpreF	Respiratory Syncytial Virus Prefusion F
SAP	Statistical analysis plan
SAS	Statistical Analysis System
SCRI	Self-controlled risk interval
SD	Standard deviation
SNF	Skilled nursing facility
Td	Tetanus diphtheria and pertussis vaccine
Tdap	Tetanus diphtheria and acellular pertussis vaccine
US	United States
VA	Department of Veterans Affairs
VAERS	Vaccine Adverse Event Reporting System
VHA	Veterans Health Administration
VINCI	VA Informatics and Computing Infrastructure
VISN	Veterans Integrated Service Networks
VISN 1	VA New England Healthcare System
VISN 17	VA Heart of Texas Health Care Network
VTE	Venous thromboembolism
WOC	Without compensation
YRR	Your Reporting Responsibilities

4. ABSTRACT

Title: A Post-Authorization Safety Study of Atrial Fibrillation Following Respiratory Syncytial Virus Vaccine (ABRYSVOTM) Among Adults Aged 18 Years and Older in the Veterans Affairs Health System

Protocol Version: 2.0; Date of Protocol: 04 December 2024

Authors: [name], PhD, White River Junction Veterans Affairs Medical Center; [name], White River Junction Veterans Affairs Medical Center; [name], MS, Pfizer, Inc.; [name], MPH, Analysis Group, Inc.; [name], Analysis Group, Inc.

Rationale and background:

ABRYSVOTM (Respiratory Syncytial Virus Vaccine [Pfizer; Study C3671013]) was authorized by the United States (US) Food and Drug Administration (FDA) on 31 May 2023 for active immunization for the prevention of lower respiratory tract disease (LRTD) caused by respiratory syncytial virus (RSV) in individuals 60 years of age and older. ABRYSVO is a bivalent recombinant protein subunit vaccine which consists of equal amounts of stabilized prefusion F (preF) antigens from the two major RSV subgroups: RSV A and RSV B (Respiratory Syncytial Virus Prefusion F [RSVpreF]). Pfizer's ongoing pivotal Phase 3 clinical trial, RENOIR (RSV vaccine Efficacy study iN Older adults Immunized against RSV disease; Study C3671013) in adults 60 years and older^{1,2} reported a vaccine efficacy of 66.7% (96.66% confidence interval [CI]: 28.8%-85.8%) in preventing RSV-associated lower respiratory tract illness with at least two signs or symptoms lasting more than one day, and 85.7% (96.66% CI: 32.0%-98.7%) in preventing RSV-associated lower-respiratory tract illness with at least three signs or symptoms. The pivotal Phase 3 study, and the totality of data from the clinical development program for older adults, provides robust evidence of a highly favorable benefit-to-risk profile.

RENOIR reported a numerical imbalance of atrial fibrillation with 10 events in the RSVpreF group (n=17,215) versus 4 events in the placebo group (n=17,069) within one month of vaccination. A medical history of atrial fibrillation was reported in 60% and 50% of the cases in the RSVpreF and placebo groups, respectively, and none of the events of atrial fibrillation were considered related to RSVpreF by the investigators. Atrial fibrillation is the most common cardiac arrythmia, where both incidence and prevalence of atrial fibrillation have been shown to increase with age and are higher in males versus females and in those of European versus African descent.

Additionally, Pfizer's pivotal Phase 3 clinical trial, MONeT (RSV IMmunizatiON Study for AdulTs at Higher Risk of Severe Illness; Study C3671023 evaluating the safety, tolerability, and immunogenicity of ABRYSVO in adults aged 18 and older at risk of developing severe RSV-associated LRTD is ongoing. The MONeT trial consists of two substudies – a double-blind randomized study among 681 adults aged 18 to 59 years old with certain chronic medical conditions (substudy A) and an open-label study among approximately 200 adults who are immunocompromised (substudy B). Positive top-line safety and immunogenicity

results were announced for substudy A in April 2024 and for substudy B in August 2024^{5,6}. Based on the inferred efficacy from the Phase 3 MONeT trial, the FDA approved ABRYSVO for the prevention of LRTD caused by RSV in individuals 18 through 59 years of age who are at increased risk for LRTD caused by RSV on 22 October 2024.⁷

Pfizer in collaboration with the US Veterans Health Administration (VHA) of the Department of Veterans Affairs (VA) and Analysis Group herein propose to conduct a post-authorization safety study (PASS) to further evaluate the risk of atrial fibrillation and supraventricular arrhythmia following ABRYSVO administration in the large-scale VHA electronic health record (EHR) database among adults 18 years and older.

This non-interventional study (NIS) is designated as a PASS and is a post-marketing commitment to the US FDA.

Research question and objectives:

Research question: What are the incidence rates of atrial fibrillation and supraventricular arrhythmia, overall and in sub-cohorts of interest, among individuals vaccinated with ABRYSVO within the US VHA system as compared to expected rates of those events?

Primary study objective:

• To estimate the incidence of atrial fibrillation following administration of ABRYSVO among adults 18 years of age and older in the VHA system

Secondary study objectives:

- To estimate the incidence of supraventricular arrhythmia following administration of ABRYSVO among adults 18 years of age and older in the VHA system
- To assess whether adults 18 years of age and older in the VHA system experience increased risk of atrial fibrillation and supraventricular arrhythmia following administration of ABRYSVO
- To estimate the incidence of atrial fibrillation and supraventricular arrhythmia in subcohorts of interest (ie, individuals with specific conditions that increase the risk for severe RSV, older age groups [60 to 69 years, 70 to 79 years, ≥80 years], individuals in VA priority group 1, individuals with dual VHA/Medicare coverage, females, individuals with co-administration with other vaccines) in the VHA system following administration of ABRYSVO
- To assess whether sub-cohorts of interest (ie, individuals with specific conditions that increase the risk for severe RSV, older age groups [60 to 69 years, 70 to 79 years, ≥80 years], individuals in VA priority group 1, individuals with dual VHA/Medicare coverage, females, individuals with co-administration with other vaccines) in the VHA system experience increased risk of atrial fibrillation and supraventricular arrhythmia following administration of ABRYSVO

Study design:

This NI PASS will assess the incidence and risk of atrial fibrillation and supraventricular arrhythmia following ABRYSVO among adults 18 years of age and older in the VHA system from 31 May 2023 to 31 May 2026. All analyses will be conducted separately for individuals 18-59 years of age and for those at least 60 years of age. Pooled analysis using combined individual-level data from both age groups may be conducted. The following retrospective, longitudinal, observational cohort study designs will be implemented:

- The incidence of atrial fibrillation and supraventricular arrhythmia following administration of ABRYSVO will be assessed in the pre-specified post-vaccination period for each outcome (eg, 0-3 days for atrial fibrillation).
- An internal comparator cohort design (ie, contemporary control design) will serve as the primary study design and will compare the incidence of atrial fibrillation and supraventricular arrhythmia among those who received ABRYSVO to the incidence in two separate random samples of contemporaneous, index date-matched controls in the VHA system based on information recorded in the VHA database:
 - 1) Primary analysis individuals who were vaccinated with another vaccine (eg, influenza vaccine or Coronavirus Disease 19 (COVID-19) vaccine on the index date (eg, +/- 30 days); ie, contemporaneous vaccinated control cohort)
 - 2) Secondary analysis individuals who were not vaccinated with any vaccine on the index date but had at least one vaccination record in the year prior to the index date (ie, contemporaneous unvaccinated control cohort)
- An self-controlled risk interval (SCRI) design, which will serve as the secondary study design, will be used to compare the incidence of atrial fibrillation and supraventricular arrhythmia during the post-vaccination risk window (eg, 0-3 days following vaccination) to the post-vaccination control window (eg, 4-10 days following vaccination) among ABRYSVO vaccinated individuals.
- Medical records review will be conducted as a separate component to validate/adjudicate cases of atrial fibrillation among ABRYSVO vaccinated individuals within the VHA system.

Population: The study population will consist of individuals with a record of at least one dose of ABRYSVO who are at least 18 years of age on the date of vaccination (ie, index date). Individuals who receive an RSV vaccine from a manufacturer other than Pfizer will be excluded from the study. Contemporary vaccinated controls will be included if they have no record of RSV vaccine and have a record for another vaccine (eg, influenza vaccine, COVID-19 vaccine, and other pre-specified vaccines such as shingles, hepatitis B) within 30 days of a corresponding ABRYSVO vaccinee's vaccination date; the control's index date will be the date of the control's non-RSV vaccine and they will be required to be at least 18 years of age on the index date. Contemporary unvaccinated controls will be included if they have no

record of any vaccine on the index date but had at least one vaccination record in the year prior to the index date; they will be assigned an index date matched to a corresponding ABRYSVO vaccinee's vaccination date and will be required to be at least 18 years of age on the matched index date. All individuals must be enrolled in (ie, not disenrolled from) VHA benefits during the 2 years prior to the index date (ie, baseline period) and have complete follow-up (ie, no disenrollment from VHA benefits, death, or receipt of RSV vaccination [for controls who may later receive any RSV vaccine only]) during the risk interval and confirmatory diagnosis window. Eligible individuals will be further classified into either the 18-59 years old age group or 60 years and older age group based on their age on the index date; contemporary vaccinated or unvaccinated controls in the 18-59 years old age group are further required to have a record for specific conditions that increase the risk for severe RSV as defined by the Centers for Disease Prevention and Control (CDC) during the baseline period (see "Subgroups" below for specific conditions).

Variables:

- Exposure: Administration of ABRYSVO will be identified based on the following:
 - o Current Procedural Terminology (CPT) code 90678, OR
 - 10 and 11-digit National Drug Codes (NDC) 0069-0207-01, 0069-0250-01, 0069-0344-01, 0069-0344-05, 0069-0344-10, 0069-0651-01, 0069-1265-10, 0069-1265-20, 0069-2465-19, 0069-2465-01, 0069-2465-10; OR
 - o Immunization records that contain data on vaccine code descriptor, vaccine manufacturer (ie, Pfizer), lot number, injection site, and date(s) of immunization.

Relevant codes will be reviewed and amended if new codes are added.

• Outcomes: The study's primary outcome, new onset atrial fibrillation, will be identified by a diagnosis code for atrial fibrillation in any setting during the 0-3 day risk interval for the primary analysis (or 0-1 day or 0-30 day risk interval for secondary analysis), or day 4-10 post vaccination control interval, followed by a confirmatory diagnosis within 30 days after the initial diagnosis and no diagnosis for atrial fibrillation or other supraventricular arrhythmia in the 2 years prior to the index date (ie, "clean window," to rule out pre-existing events). 8,9

The secondary outcome of the study will be new onset supraventricular arrhythmia, including atrial fibrillation, and will be identified in the same manner as the primary outcome.

The risk intervals were selected based on published literature and biological plausibility. ¹⁰⁻¹⁷ A safety event will be counted if it can be assigned to 1) the risk interval following ABRYSVO, 2) the post-vaccination control interval (SCRI design), or 3) risk interval for the contemporary vaccinated or unvaccinated controls.

The risk intervals for outcome evaluation for contemporary vaccinated or unvaccinated controls will be the same as for individuals who received ABRYSVO.

• Key Covariates: Baseline demographic (ie, age, sex, race/ethnicity, VHA service area, marital status) and clinical characteristics (ie, smoking, body mass index [BMI], history of anaphylaxis/allergic reactions including to vaccine components, history of hospitalizations, frailty index, Charlson Comorbidity Index [CCI], alcohol abuse, prior infections, history of atrial fibrillation prior to the baseline period, selected comorbidities, selected concomitant medications, history of immunizations, and coadministered immunizations). The final list of baseline characteristics will be defined in the statistical analysis plan (SAP) based on feasibility and availability.

Subgroups:

The following subgroups will be analyzed for the 18-59 years old age group and the 60 years and older age group:

- o Individuals in VA priority group 1;
- o Females enrolled in the VHA (pending sufficient sample size);
- O Individuals with co-administration with other vaccines (ie, influenza vaccine, COVID-19 vaccine, or other pre-specified vaccines [eg, shingles, hepatitis B]) on the same day.¹⁸

The following subgroups will be analyzed for the 60 years and older age group only:

- o Individuals with specific conditions that increase the risk for severe RSV as defined by the CDC during the baseline period, identified as those with chronic cardiovascular disease, chronic lung or respiratory disease, end-stage renal disease or dependence on hemodialysis or other renal replacement therapy, diabetes mellitus with complications, neurologic or neuromuscular conditions causing impaired airway clearance or respiratory muscle weakness, chronic liver disease, chronic hematologic conditions, severe obesity, moderate or severe immune compromise, residence in a nursing home, or other chronic medical conditions or risk factors that a health care provider determines would increase the risk for severe disease due to viral respiratory infection (eg, frailty);¹⁹ list of conditions may be updated to align with the most current CDC definition at the time of data analysis;
- o Different age groups defined by age on the index date, eg, 60 to 69 years, 70 to 79 years, ≥80 years;
- Individuals enrolled in the VHA with dual insurance coverage who are also identified in the Centers for Medicare & Medicaid Services (CMS) Medicare administrative claims data;

Data sources: The VHA is the largest integrated health care system in the US, providing both inpatient (IP) and outpatient (OP) clinical care to over 9 million Veterans enrolled at more than 170 medical centers and 1,113 community-based OP clinics.²⁰ The objectives of this study will be addressed using data from VHA's Corporate Data Warehouse (CDW), which is an integrated EHR system with a centralized data warehouse that is updated on a daily basis. The CDW lacks information on care received outside of a VHA facility. In a subgroup analysis of individuals with both VHA and Medicare coverage, CDW data will be supplemented and linked with Medicare administrative claims data at the patient level to ensure a more comprehensive evaluation of the care an individual receives.

Study size and power: All individuals who meet the eligibility criteria during the study period in the VHA database will be included. The sample size achieved will depend on the number of individuals administered ABRYSVO identified within the VHA database during the study period, which will increase over time. Data will be analyzed at two different time points to add newly vaccinated individuals and index-matched controls. Analyses using the primary internal comparator cohort design will have sufficient power (80.0%) to detect a 2-fold and 1.5-fold increased risk of safety events associated with ABRYSVO assuming a baseline rate of 33.9 events per 1,000 person-year and 4:1 matching ratio of controls to ABRYSVO vaccinees with a sample size of 37,444 and 116,493 individuals at least 60 years of age vaccinated with ABRYSVO, respectively. For individuals 18-59 years of age, based on an expected background rate of 4.4 per 1,000 person-years for incident atrial fibrillation and assuming the same matching rate of controls to ABRYSVO vaccinated individuals (ie, 4:1 ratio), a sample size of 286,730 and 892,049 individuals vaccinated with ABRYSVO is needed to detect a 2-fold and 1.5-fold increase in the incidence rate ratio (IRR), respectively with a power of 80% and a one-sided alpha level of 0.05.

Data analysis: All analyses will be conducted separately among individuals at least 60 years of age and older and among individuals 18-59 years of age. Pooled analyses among individuals 18 years of age or older may be conducted using combined individual-level data from both age groups. If heterogeneity in patient characteristics (other than age) is not observed and characteristics are considered to be sufficiently similar, then individual-level data from both age groups will be combined, and the descriptive analyses of characteristics and outcomes will be conducted using the combined dataset. If sample size is sufficient to allow comparative cohort analyses to be performed separately among individuals 18-59 years of age and individuals 60 years and older, then comparative analyses will also be performed in the pooled population.

Baseline demographics and clinical characteristics for individuals administered ABRYSVO and contemporary vaccinated or unvaccinated controls will be summarized using descriptive statistics. Descriptive statistics will also be used to summarize vaccination patterns for ABRYSVO.

Incidence rates per 1,000 patient years (and corresponding 95% CIs) will be calculated for the primary and secondary outcomes and will be compared to rates observed in the following control groups:

- Internal comparator cohorts: two random samples of contemporaneous vaccinated and unvaccinated matched controls in the VHA system. Average treatment effect among the treated (ATT) weighting, based on the propensity score (PS), will be used to ensure baseline comparability between the ABRYSVO vaccinated cohort vs. contemporary vaccinated control cohort and ABRYSVO vaccinated cohort vs. contemporary unvaccinated control cohort. ATT-weighted Cox regression with robust standard errors to account for within-subject correlation will compare the risk of safety events between cohorts. Hazard ratios and corresponding 95% CIs will be summarized.
- Self-controls: cases who experience safety events following vaccination using the SCRI design to compare the risk interval following vaccination to post-vaccination non-risk intervals in the same individual using a conditional Poisson regression model. From this model, we will report rate ratios and 95% CIs.

Diagnostic validation of identified atrial fibrillation cases among individuals administered ABRYSVO will be conducted in a randomly selected representative sample of up to 100 cases per interim/final report, as available and feasible. Positive predictive value (PPV) will be calculated as the proportion of atrial fibrillation cases deemed as true cases via adjudication among the total number of adjudicated cases. If the lower bound of the 95% CI of the PPV is less than 70% at the interim analysis, the algorithm used to identify incident atrial fibrillation using codified data may be updated in subsequent analyses and atrial fibrillation cases identified with the new algorithm will be re-adjudicated. If the lower bound of the 95% CI for PPV is equal to or greater than 70% in the interim report, chart adjudication may be waived for the final report.

If an increased risk of atrial fibrillation following ABRYSVO vaccination is observed from the analyses described above, a risk factor analysis will be conducted via logistic regression among individuals vaccinated with ABRYSVO, adjusting for baseline characteristics and co-administration of vaccines selected a priori.

Analyses may also be conducted in the subgroups of interest described above, depending on feasibility, sample size, and data availability.

Various sensitivity analyses may be conducted, including analysis of negative control outcomes. Further details and any additional sensitivity analyses will be described in the SAP.

Milestones:

 Registration in the Heads of Medicines Agencies (HMA)-European Medicines Agency (EMA) Catalogues of Real-world Data (RWD) studies: 16 August 2024

- VHA Research and Development Committee (RDC) and Institutional Review Board (IRB) approval (estimated): 31 December 2024
- Start of data collection (estimated planned date for starting data extraction for analysis): 24 February 2025
- Interim report: 25 September 2026
- End of data collection (planned date for final data cut): 30 November 2027
- Final study report: 26 May 2028

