9.5. Study Size

All individuals in the VHA database who meet the eligibility criteria as described in Section 9.2 will be included. The sample size achieved will depend on the number of individuals administered ABRYSVO identified within the VHA database during the study period, which will increase over time as the data will be analyzed at two different time points to add newly vaccinated individuals and matched controls.

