9.5.1. Power

The study population will consist of VHA enrollees 18 years of age and older without a prior history of atrial fibrillation as assessed during a 2-year baseline period. Analysis will be conducted separately among individuals at least 60 years of age and among individuals 18-59 years of age.

Of the nine million VHA enrollees,²⁰ it is estimated that 56% are at least 60 years of age⁵⁹ and one million VHA enrollees have a prior history of atrial fibrillation.⁶⁰ Based on previous studies using VHA data, it is further estimated that 85% of the eligible population will have continuous enrollment during a 2-year baseline period.⁶¹ This results in approximately 3.8 million VHA enrollees at least 60 years of age estimated as eligible for inclusion in the study. Separately, approximately 11% of adults aged 18 to 49 and 29% of those aged 50 to 64 are immunocompromised or have a chronic condition that puts them at risk for severe RSV disease.⁶² As such, an estimated 330,000 to 868,000 VHA enrollees aged 18 to 59 may be eligible for inclusion in the study.

Table 2 illustrates the estimated sample size required for the weighted Cox regression using the internal comparator cohort design for individuals at least 60 years of age and for individuals 18-59 years of age, separately. For individuals at least 60 years of age, based on an expected background rate of 33.9 per 1,000 person-years for incident atrial fibrillation reported for male Medicare beneficiaries 65 years of age and older, assuming controls (vaccinated or unvaccinated) will be matched to ABRYSVO vaccinated individuals on a 4:1 ratio, a sample size of 37,444 and 116,493 individuals vaccinated with ABRYSVO is needed to detect a 2-fold and 1.5-fold increase in the IRR with a power of 80% and a one-sided alpha level of 0.05, respectively. For individuals 18-59 years of age, based on an expected

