9.7.2. Safety Analyses

Several analyses corresponding to the internal comparator cohort and SCRI designs will be conducted to evaluate safety events associated with ABRYSVO. Analyses will be conducted among all individuals meeting the study eligibility criteria.

Incidence rates for the primary and secondary outcomes will be compared to rates observed in the following control groups:

- Internal comparator cohorts: two random samples of contemporaneous vaccinated and unvaccinated matched controls in the VHA system.
- Self-controls: cases who experience safety events following vaccination using the SCRI design to compare the risk interval following vaccination to post-vaccination non-risk intervals in the same individual.

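### Both control cohorts are random samples of unstated size (planned at 4:1) with no reason given, while other text includes all eligible people; at 60+ a larger matched control set would regain precision that weighting may cost

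*Protocol*

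**What the plan says.** The Abstract (study design) compares vaccinees with "two separate random samples of contemporaneous, index date-matched controls in the VHA system". The Abstract (data analysis) and Section 9.7.2 repeat this: "Internal comparator cohorts: two random samples of contemporaneous vaccinated and unvaccinated matched controls in the VHA system". Section 9.1 has the same wording, and Section 9.1.1 has unvaccinated controls selected at random. None of these places gives a reason for sampling or a ratio.

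Other statements point the other way. The Abstract (study size) says: "All individuals who meet the eligibility criteria during the study period in the VHA database will be included". Section 9.5 says: "All individuals in the VHA database who meet the eligibility criteria as described in Section 9.2 will be included". Section 9.7.2, which itself names the random samples, says: "Analyses will be conducted among all individuals meeting the study eligibility criteria".

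A ratio appears only in the sample size text. The Abstract refers to a "4:1 matching ratio of controls to ABRYSVO vaccinees", and Section 9.5.1 is worded as an assumption: "assuming controls (vaccinated or unvaccinated) will be matched to ABRYSVO vaccinated individuals on a 4:1 ratio". Table 2 also tabulates 2:1. Sections 9.1.1, 9.2.1 and 9.7.2.2 fix no ratio. Under Section 9.7.2.2 each control is weighted by PS/(1-PS), with truncation possible. No weight distribution or effective sample size is assumed anywhere.

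**The concern.** The number of vaccinees depends on uptake, and Section 9.5.1 already foresees a possible shortfall that would be discussed with the FDA. The number of controls is the quantity the sponsor can raise. Controls are existing records, and chart review (Section 9.7.2.4) covers only vaccinated cases, so more controls bring no extra adjudication.

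Odds weights reduce the effective number of controls. Table 2 is titled as the calculation for the weighted Cox regression but treats every control as fully informative. If the sample is drawn at the planning ratio, the primary hazard ratio could be less precise than Table 2 implies, when records that could offset the loss are available. The conflicting text also leaves open which control set is to be analysed.

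**Working it through.** **Inputs.** Section 9.5.1 and the Table 2 notes: background rate at 60+ of 33.9 per 1,000 person-years, 4-day risk interval, one-sided alpha 0.05, power 80%, and about 3.8 million eligible enrollees aged 60 or older. Not in the protocol, so assumed: the fraction f of controls that remains effective after weighting, taken as 100%, 60%, 40% and 25%.

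**Reproducing Table 2.** Expected events per control: λ = 0.0339 × 4/365 = 0.0003715. With k controls per vaccinee and rate ratio θ,

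N = (1.645 + 0.842)² × (θ + 1/k) / (λ(θ − 1)²), where the squared term is 6.1826 before rounding.

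- θ = 1.5, k = 4: 6.1826 × 1.75 / (0.0003715 × 0.25) = 116,493, as printed.
- θ = 2.0, k = 4: 37,444, as printed.
- θ = 1.5, k = 2: 133,135, as printed.
- θ = 2.0, k = 2: 41,605, as printed.

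All eight 60+ cells reproduce to within 1.

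**Changing the ratio and allowing for weighting.** Replace k by k × f. Power at fixed N is Φ((θ − 1)√(Nλ/(θ + 1/(kf))) − 1.645). For θ = 1.5 and N = 116,493:

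| Effective fraction f (assumed) | N needed at 4:1 | N needed at 16:1 | Power at 4:1 | Power at 16:1 |
|---|---|---|---|---|
| 100% | 116,493 | 104,011 | 80% | 84% |
| 60% | 127,587 | 106,785 | 77% | 83% |
| 40% | 141,456 | 110,252 | 73% | 82% |
| 25% | 166,418 | 116,493 | 67% | 80% |

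With the variance of the log hazard ratio proportional to 1/θ + 1/(kf), the standard error at f = 100% falls by about 11%: √[(0.6667 + 0.0625)/(0.6667 + 0.25)] = 0.89.

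**Ceiling.** With unlimited controls, N at θ = 1.5 falls only to 99,851 and power at 116,493 rises only to 85%. Expected vaccinee events, 116,493 × 0.0003715 × 1.5 ≈ 65, set a floor that more controls cannot lower.

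**Is the pool large enough?**
- 60+, 1.5-fold row: (3,800,000 − 116,493)/116,493 = 31.6 controls per vaccinee at most. A ratio of 16:1 needs 16 × 116,493 = 1,863,888 controls, about half of the remaining 3,683,507.
- 60+, 1.2-fold row: (3,800,000 − 603,267)/603,267 = 5.3 at most.
- 18-59, 2-fold row at 4:1: 286,730 + 1,146,920 = 1,433,650 people, against an eligible pool of 330,000 to 868,000. At that N the pool allows 0.15 to 2.0 controls per vaccinee.

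**The case against.** The strongest reply is that the protocol sets no 4:1 limit. The ratio is a planning assumption with 2:1 beside it, and the sample actually drawn may be fixed in the SAP. That stands: a reader might infer that controls are cut to 4:1, but the documents say only that they are random samples.

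A reader might also infer that sampling causes the weighting loss. It does not. The loss comes from unequal weights; in a simulation the design effect was 2.53 in the full pool and 2.52 after sampling to 4:1. Extra controls offset the loss without removing it.

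A third tempting reading is that the weighted analysis will miss its stated power by a wide margin. A log-hazard-ratio calculation for a two-sided 95% interval gives 65% and 54% at 4:1 with 40% and 25% effective. The plan's target, however, is "with a power of 80% and a one-sided alpha level of 0.05, respectively", so those figures change the test. Under the plan's own formula the values are 73% and 67%, and both depend on an effective fraction that no section supplies.

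It can also be said that the inclusion statements mainly concern vaccinees, since the Abstract goes on to say that the sample size depends on how many receive ABRYSVO. That is a fair reading of the Abstract. It is weaker for Section 9.7.2, where the all-eligible statement and the random samples stand together.

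Finally, taking every eligible control date is not free. It would lose the calendar balance that index-date matching gives, and it is undefined for unvaccinated controls, whose dates are assigned from vaccinees. This stands and shapes the fix. Section 9.5.1 also holds back comparative analyses until events suffice, which limits the harm but does not justify sampling.

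**Conclusion.** The point holds in a limited form. The protocol samples controls without a reason or a stated operative ratio, its inclusion statements do not agree with that, and Table 2 allows nothing for weighting.

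At 60+, with 116,493 vaccinees and a rate ratio of 1.5, moving from 4:1 to 16:1 is worth about 4 power points with no weighting loss. Over the assumed range of 60% to 25% effective controls it is worth about 6 to 13 points. These figures rest on the plan's formula and background rate, the assumed effective fractions, and about half of the 60+ pool having a qualifying control date. The gain is capped by vaccinee events and shrinks as uptake nears the 1.2-fold row. It does not apply at 18-59 at Table 2 sizes, though it could if uptake there is low. The documents do not show that the primary analysis is underpowered. They show an efficiency gain left unused and text that should be made consistent.

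**What to change.** 1. Reconcile the inclusion statements in the Abstract and Sections 9.5 and 9.7.2 with the random-sample wording in the Abstract and Sections 9.1, 9.1.1 and 9.7.2. State the operative ratio and the reason for any sampling.
2. At 60+, use all eligible vaccinated controls within the 30-day window, or the largest feasible index-date-matched ratio, with calendar time of the index date in the propensity score. Section 9.3.3 lists month and year only as ABRYSVO characteristics.
3. For unvaccinated controls, raise the matched ratio and keep index dates assigned from vaccinees.
4. Report the effective control sample size after weighting.
5. Keep 4:1 as the planning figure in Table 2.

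The cost is larger files, longer run time and a calendar-time term in the model. The planned robust standard errors already address people who contribute more than once. No new patients, data source or chart review is needed.
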